
Subjects with a negative HBs Ag test and tests showing results in (1), (2), or (3) do not require HBV DNA PCR qualitative testing.

- (1) HBc Ab Total (-) and HBs Ab (-): no evidence of prior infection
- (2) HBc Ab Total (-) and HBs Ab (+): immunity due to HBV vaccination
- (3) HBc Ab Total (+) and HBs Ab (+): immunity due to past infection

Subjects with HBs Ag (-), HBs Ab (-), and HBc Ab Total (+) require PCR qualitative testing for HBV DNA to determine if

- Resolved HBV infection
- False positive HBc Ab test
- Low level chronic HBV infection
- Resolving acute HBV infection

Hepatitis B testing (as described above) will be repeated for subjects of the T2T group before initiating escalation step 2. Hepatitis B testing must be performed and evaluated before adalimumab is administered. If a subject is diagnosed with active hepatitis B (acute or chronic) the subject is not eligible to receive adalimumab and should discontinue from the study.

C-Reactive Protein (CRP)

Testing for CRP will be performed on specimens collected at the designated study visits listed in Table 1.

If a subject has an elevated CRP which the investigator believes to be secondary to an AE and not due to axSpA, sites may repeat the CRP later on within the time window allowed for the respective visit following a discussion with the AbbVie Study Designated Physician. Instances where AE-related CRP elevation spans more than one study visit will be addressed on a case-by-case basis.

Erythrocyte Sedimentation Rate (ESR)

Testing for ESR will be performed on specimens collected at the designated study visits listed in Table 1. ESR will be evaluated at the site and expressed in mm/hg (1st hour). In order to enable making the decision about T2T treatment escalation at the day of the respective visit, ASDAS_{ESR} will be calculated for the purpose of decision making.

Antibodies Against CD74 CLIP

Samples will be obtained for biomarker testings at the designated study visits in Table 1.

Sample collection is described in more detail under Section 5.3.2.1. The primary biomarker is anti-CD74 CLIP antibodies.

Magnetic Resonance Imaging (MRI) of the Spine and Sacroiliac Joints

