- Patients global Assessment of Disease activity within the last week (Appendix G)
- Patient's assessment of nocturnal back pain within the last week (Appendix M)
- Patient's assessment of total back pain within the last week (Appendix N)
- Patient's global assessment of pain within the last week (Appendix O)

Health Outcomes Questionnaires

Subjects will complete the following questionnaires: ASAS Health Index (HI) (Appendix P), European Quality of Life – 5 Dimension Questionnaire (EQ-5D) (Appendix R), and Work Productivity and Activity Impairment Questionnaire – Specific Health Problem Questionnaire (WPAI-axSpA) (Appendix Q). The ASAS HI will assess the overall functioning of each subject. The EQ-5D will assess the subject's view of their health. The WPAI-axSpA will assess work related issues. These assessments should be completed prior to any other study related procedures being performed in the order outlined on Table 1.

Prior and Concomitant Therapy Assessment

Any medication that the subject is receiving at the time of Screening or receives during the study must be recorded on the source documents as well as the appropriate eCRF. Previous prescription medications or physician-administered treatments used for axSpA prior to study entry will be recorded. See Section 5.2.3 for full details regarding documentation of prior and concomitant therapy.

Ankylosing Spondylitis Disease Activity Score (ASDAS) Calculation (Treat-to-Target [T2T] Group)

The ASDAS_{ESR} will be calculated for each visit as outlined in Table 1 for subjects in the T2T group. The ASDAS_{ESR} will be calculated using the parameters listed in Appendix E of the respective visit including the ESR measurement of the respective visit.

The ASDAS_{ESR} will be automatically calculated by the eCRF upon entry of the respective parameters.

In order to enable making the decision about T2T treatment escalation on the day of the respective visit, ASDAS_{ESR} will be calculated. The subject will need to wait at the site for approximately 1 hour until the ESR result is available, the ASDAS_{ESR} is calculated, and treatment escalation decision is made.

Published ranges for disease activity states as defined by the ASDAS are: < 1.3 for "inactive disease"; ≥ 1.3 to < 2.1 for "moderate disease activity"; ≥ 2.1 to ≤ 3.5 for "high disease activity" and > 3.5 for "very high disease activity."³³

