If a subject has an elevated ESR which the investigator believes to be secondary to an AE and not due to axSpA, sites may repeat the ESR later on within the time window allowed for the respective visit following a discussion with the AbbVie Study Designated Physician. Instances where AE-related ESR elevation spans more than one study visit will be addressed on a case-by-case basis.

Enrollment and Randomization

Subjects who meet the inclusion criteria and do not meet any of the exclusion criteria will be enrolled into the Randomized Open-Label Treatment Period randomized in a 1:1 ratio to receive either T2T treatment or SOC as outlined in Section 5.1. Subjects will not be enrolled in the study if laboratory or other screening results are clinically unacceptable.

As they are enrolled into the study, subjects will be assigned unique consecutive numbers starting with 10001_ _, whereas, the first 2 digits represent the country, the next 3 digits represent the site number and the last 2 digits represent a sequential number. Site numbers will be assigned sequentially.

Dispense Study Drug

Study drug will be dispensed to subjects as outlined in Table 1 and described in more detail under Section 5.5.

Administration of Study Drug

The first time study drug is administered this will be done under direct observation in the Investigator's office to ensure proper technique as described in more detail under Section 5.5.

70-Day Follow-Up Call for Treat-to-Target (T2T) Group

Subjects of the T2T group who were on treatment with study drug adalimumab during the study but do not continue on commercially available Humira after completing or discontinuation from the study will be contacted approximately 70 days following their last dose of study drug to check for new, and update ongoing AEs or Serious AEs (SAEs) except those subjects that continue on Humira therapy after the end of study participation. Any new AEs/SAEs reported during the 70-day follow-up period should be submitted to AbbVie. The 70-day follow-up phone call will be recorded in source document only and confirmation of the contact will be faxed to AbbVie (Appendix T). Subjects that continue on adalimumab therapy after study end are not required to complete the 70-day follow-up and any new AEs should be reported through the mechanism used for all post marketing adverse experiences.

5.3.2 Measurement of Autoantibodies Against CD74 CLIP**5.3.2.1 Collection of Samples for Analysis**

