5.5.5 Blinding**5.5.5.1 Blinding of Investigational Product**

Neither the investigator(s) nor their study staff, or subjects will be blind to the treatment arm subjects are randomized to. The investigator should not influence their SOC treatment based upon knowledge and potential benefits/risks in the intensified T2T treatment arm.

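### The provision to repeat a raised ESR attributed to an adverse event stands only under the T2T heading and works only toward a lower ASDAS; if the primary ASDAS is the ESR version, responder status at Week 32 can be determined differently by arm

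*Protocol*

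**What the plan says.** The repeat provision in Protocol Section 5.3.1.1 stands under the heading "Ankylosing Spondylitis Disease Activity Score (ASDAS) Calculation (Treat-to-Target [T2T] Group"). Its trigger is: "If a subject has an elevated ESR which the investigator believes to be secondary to an AE and not due to axSpA". In that case "sites may repeat the ESR later on within the time window allowed for the respective visit", and this happens "following a discussion with the AbbVie Study Designated Physician". For longer episodes: "Instances where AE-related ESR elevation spans more than one study visit will be addressed on a case-by-case basis".

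The general ESR subsection of the same section, which covers both arms, begins "Testing for ESR will be performed on specimens collected at the designated study visits listed in Table 1. ESR will be evaluated at the site" but contains no repeat rule. The general CRP subsection does contain one, in nearly the same terms and without limit to an arm: "sites may repeat the CRP later on within the time window allowed for the respective visit".

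Four other places bear on the point:

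- **Blinding.** Section 5.5.5.1 says that neither the investigators nor their staff nor "subjects will be blind to the treatment arm subjects are randomized to". Section 5.1 adds that in the SOC arm the treating physician does not see the ASDAS computed by the eCRF. In the T2T arm it is computed and used on the day of the visit.
- **Window.** Section 5.3.1 allows 7 days either side for every visit.
- **Endpoint.** Section 5.3.3.1 defines the primary endpoint as ASDAS < 1.3 at Week 32 and does not name the ESR or CRP version. Section 3.5 describes the score as using either.
- **Formula.** Appendix E gives the ESR version only.

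**The concern.** A second measurement is available only when the first is high, so selection runs one way, toward a lower ESR and a lower ASDAS. The trigger is a judgement about cause, made by someone who knows the arm. In T2T that person also sees the calculated score, and so can see whether ESR is what holds the subject above a threshold.

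If sites follow the headings, this second chance exists for ESR in T2T and not in SOC, at every visit including Week 32. Under the ESR version of ASDAS, responders would then be determined by different rules in the two arms, and the difference favours T2T. The contrast with the CRP provision suggests that the asymmetry comes from where the text was placed rather than from a design choice. A site, however, can act only on what is written.

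**Working it through.** **1. Where each repeat rule applies**

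| Analyte | General subsection (both arms) | ASDAS subsection (T2T heading) |
|---|---|---|
| CRP | repeat of an AE-related high value allowed | – |
| ESR | no repeat rule | repeat of an AE-related high value allowed |

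**2. Can a repeat ESR change responder status?** From Appendix E:

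ASDAS = 0.08 × total back pain + 0.110 × patient global + 0.09 × peripheral pain/swelling + 0.07 × morning stiffness + 0.29 × √ESR.

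- The ESR term alone reaches 1.3 at ESR = (1.3/0.29)² = 20.1 mm/h. At or above that value the subject is a non-responder even with all four patient items at 0.
- A fall from 30 to 10 mm/h moves the ESR term from 0.29 × √30 = 1.59 to 0.29 × √10 = 0.92, a drop of 0.67.
- A fall from 20 to 10 mm/h lowers it from 1.30 to 0.92, a drop of 0.38.

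So a repeat can turn a non-responder into a responder.

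**3. How many subjects are exposed to this?** At a repeat ESR of 10, the patient items may contribute less than 1.3 − 0.92 = 0.38. Their weights sum to 0.08 + 0.110 + 0.09 + 0.07 = 0.35. The weighted average of the four items must therefore be below 0.38/0.35, about 1.1 on the 0 to 10 scale. Only subjects who are nearly free of symptoms can change status.

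**4. The plan's own figures (Section 8.2).** Dropout of 18% dilutes 20% and 40% to 0.82 × 20% = 16.4% and 0.82 × 40% = 32.8%, a planned difference of 16.4 points. The pooled-variance chi-square formula (two-sided 0.05, 80% power) gives 82 and 108 per arm against the stated 83 and 109. Fisher's exact test has power of 80.2% at 90 per arm and 80.8% at 119. The sample size reproduces and is not in question.

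**5. Illustration of the stake.** The protocol gives no frequency of repeats, so the shift is assumed. Exact enumeration of the two-sided Pearson test, 120 per arm, same true rate in both arms, net shift in T2T only:

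| Net shift to responder | Subjects of 120 | Type I error, base rate 16.4% | of which in favour of T2T | Type I error, base rate 20% | Shift ÷ 16.4-point effect |
|---|---|---|---|---|---|
| 0 points | 0 | 5.1% | 2.6% | 5.1% | 0% |
| 1 point | 1.2 | 5.6% | 4.1% | 5.5% | 6% |
| 2 points | 2.4 | 7.1% | 6.2% | 6.8% | 12% |
| 4 points | 4.8 | 12.8% | 12.5% | 11.7% | 24% |

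The 16.4% column is the relevant one, because it is the plan's control rate for the ITT analysis. An equal net shift in both arms would add no difference under the null.

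**The case against.** **The restriction to one arm is inferred.** A reader might conclude that the protocol bars the repeat in SOC. It does not: the paragraph speaks of subjects and sites in general, and its position beside the same-day escalation text has an innocent explanation. This stands as a limit on the claim. It does not remove the inconsistency with the CRP rule.

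**ESR may not enter the primary endpoint.** The general ESR subsection ties the ESR version of ASDAS to escalation decisions, Appendix E labels its formula as for reference, and CRP is collected at the same visits. If the primary ASDAS uses CRP, the repeat rule already covers both arms and the one-arm argument falls. What remains is one-way discretion by an investigator who knows the arm.

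**The text says repeat, not replace.** A reader might infer that the high value is overwritten. The protocol does not say which value counts, and choosing among values in a visit window is commonly left to the SAP. That silence alone would not be a finding. The unequal placement of a rule that the protocol does state is one.

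**There are safeguards.** The repeat needs attribution to an adverse event, discussion with the sponsor's physician, and timing within the window. It might be inferred that this physician also knows the arm, but Section 5.5.5.1 covers only investigators, staff and subjects. Equally, the text requires neither that physician's agreement nor blinding.

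**The shift is assumed and the pool is small.** Step 3 supports this. A change needs a nearly symptom-free subject with an AE-raised ESR at Week 32 that settles within the window.

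**Conclusion.** The concern holds in limited form. The ESR repeat provision is placed under the T2T heading while its CRP counterpart covers both arms. It works only toward a lower score, starts from the judgement of an investigator who knows the arm, and includes Week 32. If the primary ASDAS is the ESR version, as Appendix E implies but Section 5.3.3.1 does not state, the provision opens a route by which responder status can be changed in one arm only.

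The documents do not show that bias will occur or how large it would be. It would be tempting to read the 7.1% or 12.8% as the trial's type I error, but these figures follow only from assumed net shifts of 2 or 4 points in T2T with none in SOC. With a 1-point shift the figure is 5.6%. The change is worth making because it is cheap and closes the route whichever shift is true.

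**What to change.** 1. Name in Section 5.3.3.1 the ASDAS version used for the primary endpoint.
2. Move the ESR repeat provision to the general ESR subsection, so that it applies identically to both arms, as for CRP.
3. Record both values, flag the repeat, and report the number of repeats by arm.
4. Use the first scheduled ESR (and CRP) of the visit for the Week 32 and Week 52 ASDAS endpoints in both arms, with repeat values as a sensitivity analysis.

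The use of repeats for treatment decisions is unchanged.

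Identical wording alone may not be enough, which is the reason for item 4. The trigger is an adverse event, and the tight-control psoriatic arthritis trial cited in Section 3.8 recorded 622 adverse events (97% of patients) against 249 (80%) under standard care. A rule worded alike could still be used more often in T2T.

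The cost is a few sentences and one data flag. The downside is that some values raised by intercurrent illness stay in the primary analysis. If adverse events are more frequent in T2T, this would happen more often there and make the comparison slightly conservative. The choice of first over repeat value is therefore open to some debate; the need for one rule in both arms is not.

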5.3.2.2 Handling/Processing of Samples for the Detection of Autoantibodies Against CD74 CLIP

Within 2 hours after the blood sample was obtained, the tube will be spun down (see laboratory manual for detailed instructions). The supernatant will be frozen immediately and stored at at least –20°C. The serum samples will be pseudonymized using the subject's unique identification code and initially stored at the site where the subject was recruited.

5.3.2.3 Disposition of Samples for the Detection of Autoantibodies Against CD74 CLIP

Shipment of pseudonymized samples to the central laboratory will be done by a courier service on dry ice per the central laboratory instruction manual when 20 sera have been collected or every 3 months, whatever is earlier. An inventory of the samples included will accompany the package.

The shipment address for the samples is:

The samples will be stored in the central lab at at least –70°C until they are used for the study specific analysis of the antibodies against CD74 CLIP. Remaining rest of serum samples will be discarded.

5.3.3 Efficacy Endpoints**5.3.3.1 Primary Efficacy Endpoint**

The primary efficacy endpoint is the clinical disease activity at Week 32 as measured by the percentage of subjects in ASDAS inactive disease (ASDAS < 1.3).

5.3.3.2 Secondary Endpoints

Secondary endpoints include the following:

At Week 32 and Week 52

- Quality of life by the EQ-5D Questionnaire
- WPAI-axSpA
- Overall functioning by ASAS HI
- Disease activity as measured by BASDAI
- Percentage of subjects achieving 50% improvement in BASDAI (BASDAI 50 response)
- Function – Represented by the BASFI NRS score (0 to 10)
- Disease activity measured by ASDAS
- ASDAS major improvement
- ASDAS clinically important improvement
- Percentage of subjects in ASDAS inactive disease (ASDAS < 1.3)
- Percentage of subjects with low disease activity (ASDAS < 2.1)
- Percentage of subjects with moderate disease activity (ASDAS \geq 1.3 to < 2.1)
- Percentage of subjects with high disease activity (ASDAS \geq 2.1 to < 3.5)
- Percentage of subjects with very high disease activity (ASDAS \leq 3.5)
- ASAS 20, ASAS 40, and ASAS Partial Remission
 - ASAS20 response: improvement of \geq 20% and absolute improvement of \geq 1 unit (on a scale of 0 to 10) from Baseline in \geq 3 of the following 4 domains, with no deterioration in the remaining domain (defined as a worsening of \geq 20% and a net worsening of \geq 1 unit)

- Patient's Global Assessment (PTGA) – Represented by the PTGA-disease activity NRS score (0 to 10)
- Pain – Represented by the patient's assessment of total back pain NRS score (0 to 10)
- Function – Represented by the BASFI NRS score (0 to 10)
- Inflammation – Represented by the mean of the 2 morning stiffness-related BASDAI NRS scores (mean of items 5 and 6 of the BASDAI [0 to 10])
 - ASAS40 response: improvement of $\geq 40\%$ and absolute improvement of ≥ 2 units (on a scale of 0 to 10) from Baseline in ≥ 3 of the 4 domains above in ASAS20 with no deterioration in the potential remaining domain
 - ASAS partial remission: absolute score of < 2 units for each of the 4 domains identified above in ASAS20
- Active inflammation as measured by magnetic resonance imaging of the sacroiliac joints and the spine (Berlin MRI scores for MRI of the SI joint and spine)
- Physician's Global Assessment of Disease Activity
- Patient's Global Assessment of Disease Activity
- Patient's Global Assessment of Pain
- Swollen Joint Count (66 joints)
- Tender Joint Count (68 joints)
- Change from Baseline in MASES
- Change from Baseline in Dactylitis count (0 – 20)
- Change from Baseline in BASMI_{lin}
- Anterior uveitis

Other variables to be analyzed at various time points including Week 32 and Week 52 include:

- C-reactive Protein
- Erythrocyte sedimentation rate

- ASDAS course over time
- BASDAI course over time

5.3.3.3 Exploratory Endpoints

- Serum autoantibodies against CD74 CLIP
- Reduction of disease progression (as measured by MRI of the sacroiliac joints and the spine)

5.3.4 Safety Variables

Screening assessments will include medical history, vital signs, physical examination, and clinical laboratory tests. The following safety evaluations will be performed during the study: medical history and concomitant medication review, AE monitoring, assessments of vital signs, physical examination and laboratory tests.

5.4 Removal of Subjects from Therapy or Assessment

5.4.1 Discontinuation of Individual Subjects

A subject may withdraw from the study at any time. The Investigator may discontinue any subject's participation prematurely for any reason, including an adverse event, safety concerns or failure to comply with the protocol. See section 6.1.7 for toxicity management criteria.

Subjects will be withdrawn from the study immediately if any of the following occurs:

- Clinically significant abnormal laboratory result(s) or adverse event(s), as determined by the Investigator in consultation with the AbbVie Study Designated Physician.
- The Investigator believes it is in the best interest of the subject.
- The subject requests withdrawal from the study.
- Inclusion and exclusion criteria violation was noticed after the subject started study drug, when continuation of the study drug would place the subject at risk

as determined by the AbbVie Study Designated Physician (Section 5.2 and Section 7.0).

- Introduction of prohibited medications or dosages when continuation of the study drug would place the subject at risk as determined by the AbbVie Study Designated Physician.
- Subject is non-compliant with TB prophylaxis.
- The subject becomes pregnant while on study.
- Subject has dysplasia of the gastrointestinal tract or a malignancy, except for localized non-melanoma skin cancer. Discontinuation for carcinoma in situ of the cervix is at the discretion of the Investigator.
- Subject is diagnosed with lupus-like syndrome, multiple sclerosis or demyelinating disease.
- Subject is significantly non-compliant with study procedures which would put the subject at risk for continued participation in the trial, as determined by the Investigator, in consultation with the AbbVie Study Designated Physician.

If, during the course of the study, the subject prematurely discontinues from the study, the procedures outlined for the Discontinuation Visit must be completed within 2 weeks of the last dose of study drug (if applicable), and, if possible, prior to the initiation of another therapy. However, these procedures should not interfere with the initiation of any new treatments or therapeutic modalities that the Investigator feels are necessary to treat the subject's condition. Following discontinuation of the study drug, the subject will be treated in accordance with the Investigator's best clinical judgment.

A final phone call will be made to subjects of the T2T group who were on treatment with study drug adalimumab during the study but do not continue on commercially available Humira after discontinuation from the study approximately 70 days after the end of their Treatment phase (i.e., their Week 52 visit) or – in case of premature discontinuation – their Discontinuation Visit to determine the status of any ongoing AEs/SAEs or the occurrence of any new AEs/SAEs unless not required as outlined in Section 5.3.1.1.

All attempts must be made to determine the date of the last dose of study drug and the primary reason for premature discontinuation. The information will be recorded on the appropriate eCRF page.

For subjects that are considered lost to follow-up, reasonable attempts must be made to obtain information on the final status of the subject. As a minimum, two phone calls must be made and one certified letter must be sent. The attempts should be documented in the subject's source documents.

